### 1.2.2 MDMA

MDMA is a ring-substituted phenylisopropylamine derivative invented by Merck pharmaceutical company in 1912 [25, 26]. Similar to SSRIs, MDMA binds to the monoamine transporters, with the greatest affinity for the serotonin transport (SERT). MDMA also enhances synaptic levels of serotonin, and to a lesser extent norepinephrine and dopamine, by vesicular carrier-mediated release and reuptake inhibition of these neurotransmitters [27-33]. MDMA increases levels of affiliative neurohormones oxytocin and vasopressin, which is associated with increased trust and attenuation of reactivity to threatening cues, and cortisol and prolactin. The indirect effects of MDMA on central and peripheral neurohormone release contribute to a novel mechanism that may help regulate the HPA axis, which would treat the core psychopathology of PTSD for a durable remission.

Onset of MDMA effects occurs ~0.5 to 1 hour after oral administration, and peak effects occur 1.25 to 2 hours after the initial dose. Effects of the initial dose last 3 to 6 hours, which is extended to 5 to 8 hours with a supplemental half-dose administered 1.5 to 2 hours post initial dose. Orally administered MDMA has a half-life of 7 to 9 hours in humans. Unlike approved PTSD medications, therapeutic effects of MDMA have a rapid onset, and do not require daily dosing or a steady state in the blood to be effective. Thus, the effects of MDMA are distinct from and work through different mechanisms than anxiolytics and SSRIs. Furthermore, there is no evidence that limited doses of MDMA in controlled clinical settings creates a physical dependence or drug seeking behavior. Previous studies of polydrug users have found a small percentage of people exhibit problematic use of Ecstasy (material represented as containing MDMA) [34, 35]. Studies of regular or problematic Ecstasy users indicate that on average, regular use occurs no more often

than once a week [36]. Hence, MDMA is said to have moderate abuse potential in non-medical settings, and low abuse potential in clinical settings. See the Investigator's Brochure (IB) for a more detailed explanation.

# 1.2.3 MDMA-Assisted Psychotherapy for PTSD

Many psychotherapies for PTSD involve the induction and extinction of abnormal autonomic responses through revisiting traumatic experiences in psychotherapy with an appropriate level of emotional engagement [20]. To be effective, exposure must be accompanied by a degree of emotional engagement or "fear activation" while avoiding dissociation or overwhelming emotion [37]. This has been referred to as working within the "optimal arousal zone" or "window of tolerance" [38-40].

The combined neurobiological effects of MDMA increase compassion for self and others, reduce defenses and fear of emotional injury, and enhance communication and introspection. MDMA produces anxiolytic and prosocial effects, which counteract avoidance and hyperarousal in the context of therapy. PTSD increases amygdala activity, causing heightened encoding of fearful memories and decreases blood flow in the prefrontal cortex. In contrast, MDMA acutely decreases activity in the amygdala [41], and there is some indication that MDMA may increase activity in the prefrontal cortex (PFC) [42]. Another study showed increased functional connectivity between the amygdala and hippocampus, and decreased connectivity between the amygdala and PFC [43]. Brain imaging after MDMA indicates less reactivity to angry facial expressions and greater reward in happy faces [41], compatible with its reported reduction in fear or defensiveness, and counteracts the stimulation of the amygdala observed in animal models of conditioned fear, a state similar to PTSD [44-46]. The reduction in stress-induced activation of the amygdala may be supported and enhanced by interacting with the therapy team during and after the MDMA experience. The subjective effects of MDMA create a productive psychological state that enhances the therapeutic process. MDMA enhances perceived self-authenticity [47] and a naturalistic study suggests that it can increase self-compassion [48], effects that may support and contribute to the therapeutic process. MDMA is capable of inducing unique psychopharmacological effects, including decreased fear and increased wellbeing, sociability, interpersonal trust, acceptance of self and others, and ability to address these issues without extreme disorientation or ego loss due to alert state of consciousness. These factors taken together can provide the opportunity for a corrective emotional experience.

A combined treatment of MDMA and psychotherapy may be especially useful for treating PTSD because MDMA can attenuate the fear response of a perceived threat to one's emotional integrity and decrease defensiveness without blocking access to memories or preventing a deep and genuine experience of emotion [49-52]. Elimination of these conditioned fear responses can lead to more open and comfortable communication about past traumatic events and greater access to information about them [53]. Participants are able to experience and express fear, anger, and grief with less likelihood of feeling overwhelmed by these emotions. In healthy controls, MDMA reduces reactivity to unpleasant memories [54]. MDMA seems to engender internal awareness that even painful feelings that arise are an important part of the therapeutic process. In addition, feelings of empathy, love, and deep appreciation often emerge, along with a clearer perspective of the trauma as a past event, a more accurate perspective about its significance, and a heightened awareness of the support and safety that exists in the present. As a result, MDMA-assisted psychotherapy may enable participants to restructure their intra-psychic realities and develop a wider behavioral and emotional repertoire with which to respond to anxiogenic stimuli.

The therapeutic method is described in further detail in the Treatment Manual of MDMA-Assisted Psychotherapy, which the sites and therapy teams will be trained on prior to the study.

# 1.2.4 Previous Clinical Experience with MDMA

MDMA-assisted psychotherapy is a novel treatment package that combines psychotherapeutic techniques with the administration of MDMA as a pharmacological adjunct intended to enhance certain aspects of psychotherapy. Chemists Shulgin and Nichols were the first to report on the effects of MDMA in humans [55], with 80 to 160 milligrams (mg) MDMA required to produce desired subjective effects in humans [55, 56]. MDMA was found to robustly influence human emotional status in a unique way [55] without adversely affecting physiological functions or perception, such as visual perception or cognition [57-60]. In the 1970s, psychotherapists used MDMA-assisted psychotherapy to treat psychological disorders, including anxiety, even though the drug had not been studied controlled clinical trials [61]. Legal therapeutic use continued until its placement on the U.S. list of Schedule 1 substances in 1985 [50, 53, 62]. An estimated 500,000 doses of MDMA were administered during psychotherapy and personal growth sessions in North America prior to its scheduling [50, 63]. A few uncontrolled human studies of MDMA assessing safety in a controlled setting occurred in the 1980s [64, 65].

Controlled human studies for clinical development of MDMA commenced in the mid-1990s with a MAPS-funded investigator-initiated Phase 1 dose-response safety study [66, 67]. Starting in 2000 in Spain, MAPS funded a Phase 2 investigator-initiated dose-response effect and safety pilot study in participants with PTSD that was terminated early due to political pressure. This study enrolled six participants, with four receiving a single session of MDMA-assisted psychotherapy without any safety concerns and with some PTSD symptom reduction [52]. These studies formed the basis of clinical experience with MDMA prior to studies subsequently conducted under a MAPS IND with FDA.

MAPS initiated an international series of Phase 2 clinical trials to develop the medical use of MDMA-assisted psychotherapy for patients with chronic, at least moderate PTSD (CAPS-4 score: 50+), with at least 6 months of symptoms. Participants were not excluded for having more than one traumatic event, or for having tried, not tolerated, or refused an SSRI or serotonin-norepinephrine reuptake inhibitor (SNRI) prescribed for PTSD. Outcomes from six Phase 2 studies with evaluable data have been promising and have generated a range of methodological information for the design of future studies.

Results from two Phase 2 studies have been published: one study in the U.S. with a long-term follow-up (LTFU) conducted an average of 3.8 years after the final MDMA-assisted psychotherapy session (MP1) [51, 68] and one in Switzerland (MP2) [69, 70]. MP1 was followed by a small open-label extension study examining the treatment of relapse in three participants with a single MDMA-assisted psychotherapy treatment and a 12-month follow-up (MP1E2). Three additional studies have completed treatments (MP8, MP9, MP12) and two international studies were terminated early for logistical reasons with partial datasets (MP3, MP4). These studies tested a range of designs, such as a placebo control (MP1, MP4), low dose MDMA comparator control (MP2, MP9), and three-arm dose response studies (MP8, MP12). Findings from a dose-comparison study at the same site in military veterans, firefighters and police officers (MP8) have now been published and confirm findings reported in the initial studies [71]. MP4 was terminated early due to delays in regulatory approval and enrollment timelines, with available efficacy data presented without a formal analysis. MP3 was terminated early by the sponsor due to inadequate data collection procedures at the site and insufficient therapy team training; efficacy data are not available for these reasons (MP3 is excluded from Phase 2 data).

Intent-to-treat (ITT) analysis of primary efficacy and safety data from six MAPS-sponsored MDMA PTSD Phase 2 clinical trials worldwide (MP1, MP2, MP4, MP8, MP9, MP12) consisting

of 107 blinded participants with chronic PTSD was completed in 2016. In these studies, PTSD, independent of cause, appears treatable with a two- t three-session treatment package of MDMA-assisted psychotherapy. As of 01 October 2021 with 358 individuals exposed to MDMA in the sponsor's development program across various indications and at least 1799 participants in MDMA research studies conducted without sponsor support, the sponsor has observed an acceptable risk-benefit ratio for MDMA-assisted psychotherapy. Across Phase 2 studies initial doses of 75 mg-125 mg MDMA were statistically superior to 0 mg to 40 mg MDMA based on a t-test of difference in CAPS-4 severity scores from Baseline to 1 to 2 months after two to three blinded experimental sessions (p<0.001). The dropout rate across studies was 7.5% (8 of 107). Large placebo-subtracted effect sizes (Cohen's d 0.9), initial indications of efficacy, and favorable safety outcomes support expanding the research initiative to encompass a larger sample of participants with PTSD in a Phase 3 program.

A comprehensive review of MDMA research can be found in the IB supplied by the sponsor. This document should be reviewed prior to initiating the protocol.

## 2.0 Protocol Objectives

The overall objective of this study is to use standard clinical measures to explore the safety and effects of open-label manualized MDMA-assisted psychotherapy with a flexible dose of MDMA in participants with severe PTSD, and to serve as an opportunity for supervision of therapy teams selected to conduct Phase 3 MDMA-assisted psychotherapy research.

# 2.1 Primary Objective and Primary End Point

The primary objective of this study is to evaluate the effect of MDMA-assisted psychotherapy on PTSD, as measured by the estimand of change in CAPS-5 Total Severity Score from Baseline (Visit 3) to 13 weeks post Baseline (Visit 14).

The primary endpoint is the change in CAPS-5 Total Severity Score from Baseline (Visit 3) to 13 weeks post Baseline (Visit 14).

### 2.2 Secondary Objective and Secondary End Point

The secondary objective is to evaluate the effect of MDMA-assisted psychotherapy for PTSD in clinician-rated functional impairment, as measured by the mean change in Sheehan Disability Scale (SDS) item scores from Visit 3 (Baseline) to 13 weeks post Baseline (Visit 14).

The secondary endpoint is the mean change in Sheehan Disability Scale (SDS) item scores from baseline (Visit 3) to 13 weeks post Baseline (Visit 14).

### 2.3 Safety Objectives

The overall safety objective is to assess severity, incidence and frequency of AEs, AEs of Special Interest (AESIs), and Serious Adverse Events (SAEs), concomitant medication use, suicidal ideation and behavior, and vital signs to support the package insert for MDMA-assisted psychotherapy. The following safety objectives will evaluate the safety of MDMA-assisted psychotherapy.

1. Assess incidence of AEs during Experimental Sessions that may be indicative of a medical complication of the Investigational Product (IP), such as clinical signs and

- symptoms of chest pain, shortness of breath, or neurological symptoms or any other signs or symptoms that prompt additional vital sign measurements.
- 2. Assess incidence of AEs by severity.
- 3. Assess incidence of Treatment Emergent AEs (TEAEs) by severity.
- 4. Assess incidence of TEAEs by severity taken during an Experimental Session and through 2 days after IP administration.
- 5. Assess incidence of AESIs, defined as AEs specified in the protocol related to cardiac function and abuse liability.
- 6. Assess incidence of AEs by severity categorized as leading to discontinuation of IP, resulting in death or hospitalization, and continuing at Study Termination.
- 7. Assess incidence of SAEs.
- 8. Assess incidence of psychiatric concomitant medications taken during an Experimental Session and through 2 days after IP administration.
- 9. Assess incidence of any psychiatric concomitant medications taken during the Treatment Period.
- 10. Assess incidence of serious suicidal ideation and positive suicidal behavior assessed with the Columbia Suicide Severity Rating Scale (C-SSRS).
- 11. Assess mean changes in blood pressure, heart rate, and body temperature from pre-IP administration to end of each Experimental Session.

# 2.4 Exploratory Objectives

These objectives may be explored to characterize participants receiving MDMA-assisted psychotherapy to support the primary objective:

- 1. Explore the effect of presence of secondary traumatic stressors (LEC-5) on the CAPS-5 Total Severity analyses
- 2. Explore changes within-participants in PTSD symptom clusters of re-experiencing, avoidance, negative alterations in cognition and mood, and hyperarousal, as measured by changes in CAPS-5 subscale scores from Visit 3 (Baseline) to Visit 14 (13 weeks post Baseline)
- 3. Explore the effect of adverse childhood experiences (ACE) on the CAPS-5 Total Severity analyses
- 4. Explore changes in:
  - Dissociative symptoms associated with PTSD (DSP-I)
  - Depression (BDI-II)
  - Chronic pain (CPGS)
  - Quality of life (EQ-5D-5L)
  - Self-compassion (SCS)
  - Addictive behaviors including: Alcohol use (AUDIT), Drug use (DUDIT) and Nicotine use (SRNU)
  - Eating habits (EAT-26)
  - Healthcare utilization (UFEC) and economic productivity
  - Subjective effects (SE)

## 3.0 Eligibility Criteria

At the completion of Screening, participants must meet all eligibility criteria (except Inclusion Criterion #13 listed below) and agree to all lifestyle modifications to be enrolled. Each participant will then enter the Preparatory Period which includes medication tapering, if needed, and non-drug Preparatory Sessions. The Preparatory Period ends with Enrollment Confirmation. A participant's enrollment will be confirmed once they have completed medication tapering, have a

confirmed PTSD diagnosis per the CAPS-5 assessment and a Total Severity Score of 35 or greater, continue to agree to all lifestyle modifications, and continue to meet all eligibility criteria.

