### Medical History

- 16. Have a history of any medical condition that could make receiving a sympathomimetic drug harmful because of increases in blood pressure and heart rate. This includes, but is not limited to, a history of myocardial infarction, cerebrovascular accident, or aneurysm. Participants with other mild, stable chronic medical problems may be enrolled if the site physician, PI, and Medical Monitor agree the condition would not significantly increase the risk of MDMA administration or be likely to produce significant symptoms during the study that could interfere with study participation or be confused with side effects of the IMP. Examples of stable medical conditions that could be allowed include, but are not limited to Diabetes Mellitus (Type 2), Human Immunodeficiency Virus (HIV) infection, Gastroesophageal Reflux Disease (GERD), etc. Any medical disorder judged by the investigator to significantly increase the risk of MDMA administration by any mechanism would require exclusion.
- 17. Have a diagnosis of uncontrolled hypertension, defined as repeated readings of ≥140 millimeters of mercury [mmHg] systolic or ≥90 mmHg diastolic. The diagnosis may be confirmed by repeated clinic measurements or home blood pressure monitoring if clinically indicated per European Society of Cardiology (ESC) guidelines.
- 18. Have a history of ventricular arrhythmia at any time, other than occasional premature ventricular contractions (PVCs) in the absence of ischemic heart disease.
- 19. Have Wolff-Parkinson-White syndrome or any other accessory pathway that has not been successfully eliminated by ablation.
- 20. Have a history of arrhythmia, other than premature atrial contractions (PACs) or occasional PVCs in the absence of ischemic heart disease, within 12 months of screening. Participants with a history of atrial fibrillation, atrial tachycardia, atrial flutter or paroxysmal supraventricular tachycardia or any other arrhythmia associated with a bypass tract may be enrolled only if they have been successfully treated with ablation and have not had recurrent arrhythmia for at least one year off all antiarrhythmic drugs, and confirmed by a cardiologist.
- 21. Have a marked Baseline prolongation of QT/QTc interval (For purposes of eligibility, this is defined as repeated demonstration of a QT interval corrected using Fridericia's formula [QTcF] >450 milliseconds [ms]).

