# Leading up to Experimental Sessions

- Agree to take nothing by mouth except alcohol-free liquids after 12:00 A.M. (midnight) the evening before each Experimental Session.
- Refrain from the use of any psychoactive medication not approved by the research team from Baseline through Study Termination.
- Agree not to use caffeine or nicotine for 2 hours before and at least 6 hours after the initial dose during each Experimental Session.
- Are willing to comply with medication requirements per protocol (refer to Section 11.0 Concomitant Medications). Medications will only be discontinued after enrollment per clinical judgment of the site physician in consultation with the prescribing physician.
- Are able to decrease dose of allowable opiates (per Section 11.0 Concomitant Medications), if used for pain management, leading up to the Experimental Session in order to avoid taking the medication for at least 12 hours prior to the initial IP administration and 24 hours after. During this period, the participant will be allowed to take the medication if needed for intolerable pain flare-ups.
- Agree that, for 1 week preceding each Experimental Session to refrain from:
  - o Taking any herbal supplement (except with prior approval of the research team)
  - Taking any nonprescription medications (with the exception of non-steroidal anti-inflammatory medications or acetaminophen unless with prior approval of the research team).
  - Taking any prescription medications (with the exception of birth control pills, thyroid hormones, or other medications approved by the research team).

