## 4.2 Planned Duration of Study

Full screening may take 2 to 6 weeks after completion of phone screening, where performed. The Preparatory Period begins at enrollment and can be as brief as 2 weeks. Depending on medication tapering could be as long as 11 weeks to ensure an appropriate medication washout of at least five half-lives of pre-study psychiatric medications and active metabolites, and at least one additional week for stabilization.

Enrollment Confirmation takes place at the completion of the Preparatory Period, at which time the Treatment period will commence. The approximate 8-week Treatment Period will consist of two Experimental Sessions 3 to 5 weeks apart with associated non-drug Integrative Sessions and CAPS-5 assessment.

After the final Integrative Session 2.3 (Visit 13), participants will enter follow-up with no study visits for approximately 4 weeks, after which the Primary Outcome CAPS-5 T3 assessment will take place (Visit 14). Although there are allowable windows for all visits throughout the protocol, the overall timelines should comply with the target timing of the Primary Outcome CAPS-5 T3 assessment, which must be completed 13 weeks (+/-3 weeks) post Baseline, even if the maximum possible visit windows were used between visits. Other visits should be scheduled to ensure the timing of the Primary Outcome CAPS-5 T3 assessment is appropriate. The Study Termination visit follows 1 to 9 days after the final CAPS-5 assessment.

The minimum time that a participant who completes all study visits from Screening to Study Termination will be in the clinical trial is 14 weeks and the maximum is 27 weeks. The average participant is expected to complete the study in 17 weeks. Any delays between visits outside of the protocol-defined windows may result in a corresponding extension of study duration and should be documented as a deviation as appropriate.

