**Table 5: Time and Events – Screening and Preparatory Study Procedures** 

			ing Period 6 weeks)		Prep	Preparatory Period w/ Enrollment Confirmation (2 to 11 weeks)							
		Screening	,	Enrollment		ratory	Baseline CAPS-5 T1	Baseline & Enrollment Confirmation					
Visit	Phone Screening	Screening	IR Screening	V0	V1	V2	V3	V4					
Visit Description	Phone Calls	In-person Visits & Labs	Tele- assessment	Enrollment	Prep. 1	Prep. 2	Tele- assessment	Prep. 3 & Enrollment Confirmation					
Visit Timing	Prior to Initial Screening	Over 3 weeks (-2 /+1 weeks)	2 days after initial eligibility met (+7 days)	2 days post IR Screening (+12 days)	Within 1 week of V0 (0 to 12 days)	2 to 21 days of V1	Post V2 & Taper	3 to 6 days after V3; 1 to 4 days before V5					
Initial Phone Screen	√A												
Informed Consent	Send Copy	✓											
Follow-up Phone Screen	√												
Assess Eligibility	✓	√		✓	✓	√		✓					
Medical/Psychiatric History	√ B	✓			√	√		✓					
Past/Current Medication & Adherence	√	√			√	√		√					
Weight, Blood Pressure, Pulse, Temperature		√											
Physical Exam		✓											
ECG C & Rhythm Strip		✓											
Clinical Lab Tests		✓											
Drug Test D		✓						✓					
Pregnancy Test E		✓						✓					
Digital Recording of Visit			√		✓	√	√	✓					
Medication Taper				✓	✓	✓							
Study Enrollment				✓				✓ Confirmed					
AE Assessment F				✓	✓	√		√					
90-min Preparatory Session					✓	✓		✓					
Phone Call Follow-up G						√							

A In Germany phone screening is not permitted

<sup>B At Screening, collect data on previous hospitalizations, healthcare utilization and economic productivity. Request participants to obtain medical/psychiatric records to bring to the next in-person screening visit.

<sup>C ECG to be conducted at any time if clinically indicated.

<sup>D In the UK, also includes testing for alcohol.

<sup>E PABP Only. Urine or serum (UK: serum only).

F Adverse Events (Aes) Assessment includes collecting Serious Adverse Events, Aes of Special Interest, Aes of Psychiatric Status, Aes requiring medical advice or attention, Aes that indicate withdrawal of a participant, and all other Aes

<sup>G If needed, call participant to confirm medication tapering and stabilization is complete prior to Visit 3

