• If the potential participant has well-controlled hypertension and no other evidence of cardiovascular or cerebrovascular disease by history, physical exam or ECG, and if the investigator judges their overall health and other cardiovascular risk factors to be acceptable (family history, smoking, lipid levels, body weight, level of physical activity), they will be referred for stress test with either echocardiography or nuclear imaging, and for carotid ultrasound. If these tests fail to reveal evidence of significant vascular disease or other cardiac disease, the person may be enrolled if there are no other contraindications. Additional cardiovascular testing to confirm eligibility may be performed in consultation with Medical Monitor. Participants taking one or more antihypertensives may be enrolled in the study. The investigators will record and review medications used to control hypertension prior to enrollment.

Additional visits or repeat assessments (in person, at home, by telephone, or via tele-assessment) may be scheduled at the discretion of the study staff to collect more information for determining eligibility or to discuss study expectations with the potential participant. For instance, at home blood pressure measurements may be required to corroborate or rule out undiagnosed hypertension or to determine if an ongoing diagnosis of hypertension is controlled per the ESC guidelines, and as required per the eligibility criteria of this protocol.

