## 7.2 Preparatory Period with Enrollment Confirmation

Participants will undergo three Preparatory Sessions (Visits 1, 2, and 4) lasting approximately 90 minutes with the therapy team prior to the first Experimental Session. The Preparatory Period will be initiated within 12 days of Visit 0 and last 2-11 weeks, depending on duration of medication tapering. There must be at least 48 hours between Preparatory Sessions. The minimum time to complete the Preparatory Period is 2 weeks. The Preparatory Period will also include the Baseline CAPS-5 assessment (Visit 3), which will be assessed by an IR.

Adherence criteria for Preparatory Sessions should be followed per the Treatment Manual. In these visits, the therapy team will work with the participant to prepare for MDMA-assisted psychotherapy, begin building therapeutic alliance, and promote a safe set and setting for confronting trauma-related memories, emotions, and thoughts.

## 7.2.1 Preparatory Session 1 and Preparatory Session 2

Preparatory Sessions during the Preparatory Period will focus on psychoeducation about PTSD, building safety for the therapeutic relationship, developing the therapeutic alliance, obtaining the background for the trauma, and preparing the participant for the first Experimental Session. Telephone calls may be scheduled between visits if indicated for tapering, safety, or any further questions about medical history.

- Preparatory Session 1 (Visit 1) will occur within 1 week (0 to 12 days) of Visit 0. The visit timing should take into account appropriate times for monitoring medication tapering.
- Preparatory Session 2 (Visit 2) will occur within 3 weeks of Visit 0 and at least 2 days after Visit 1. The visit timing should take into account appropriate times for monitoring medication tapering. Visit 2 must take place at least 2 days after and within 3 weeks of Preparatory Session 1 (Visit 1)

• If tapering is ongoing at Preparatory Session 2 (Visit 2), the site team will schedule a telephone call after tapering and stabilization are complete to confirm that the participant is eligible for the Baseline CAPS-5 assessment. If tapering is complete or not needed, the site team will confirm eligibility and schedule Baseline CAPS-5 T1 (Visit 3) and Preparatory Session 3 (Visit 4) as soon as possible.

At each 90-minute psychoeducation and psychotherapy Preparatory Session, the therapy team will:

- Record the therapy session.

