#### 7.2.3 Baseline: Preparatory Session 3 and Enrollment Confirmation

Prior to Visit 4, the site team will review the results of the IR visit to ensure that the CAPS-5 Total Severity Score is at least 35. Visit 4 should be scheduled within 6 days of the Baseline CAPS-5 assessment but ideally will take place as close to Experimental Session 1 (Visit 5) as possible, but not on the same day.

At Visit 4, the site team will confirm eligibility by reassessing specified eligibility criteria and ensuring that the participant continues to agree to all lifestyle modifications. If the participant continues to be eligible for the study, enrollment will be confirmed (after approval from the Medical Monitor for the initial participants until confidence is established). If any requirements are not met before or during Visit 4, the participant will be considered a Pre-Dosing Early Termination.

For eligible participants at Visit 4, qualified site staff will ensure at least 3 hours are scheduled for the visit and:

- Collect urine sample for pregnancy test from PABP.
- Perform urine drug test.
- Perform alcohol test (UK only).
- Administer Since Last Visit C-SSRS to determine suicidal risk.
- Actively support participant in the completion of Baseline self-reported measures:
  - o PCL-5- ensure assessment is in relation to index trauma
  - o ACE
  - o BDI-II
  - o CPGS
  - o EQ-5D-5L
  - o SCS
  - o SRNU
  - o EAT-26
  - o UFEC and economic productivity

Completion of the measures does not need to be recorded.

- Complete the third 90-minute Preparatory Session (as described in Section 7.2.1 Preparatory Sessions 1 and 2) with the purpose of confirming all enrollment is met and completing final preparation for the first Experimental Session.
- Remind the participants of lifestyle modifications, including fasting and refraining from using psychoactive or non-approved medications, pertinent prior to the Experimental Session per Section 3.3 Lifestyle Modifications.
- Schedule Visit 5.

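### Blood pressure is an eligibility criterion that must still hold at Enrollment Confirmation, but none is routinely scheduled between Screening and Visit 4, and a high pre-dose reading triggers no repeat or physician review before the initial dose

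*Protocol*

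**What the plan says.** Protocol section 3.0 makes Enrollment Confirmation conditional on participants who "continue to agree to all lifestyle modifications, and continue to meet all eligibility criteria". Section 7.2.3 places the check: "At Visit 4, the site team will confirm eligibility by reassessing specified eligibility criteria". It does not list which criteria are meant.

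Exclusion 17 (section 3.2) is a blood pressure criterion: uncontrolled hypertension, defined by repeated readings of at least 140 mmHg systolic or 90 mmHg diastolic. It adds that "The diagnosis may be confirmed by repeated clinic measurements or home blood pressure monitoring if clinically indicated".

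In Table 5 the row "Weight, Blood Pressure, Pulse, Temperature" is ticked once, at in-person Screening. The Visit 4 list in 7.2.3 contains a pregnancy test, drug test, alcohol test (UK), C-SSRS and questionnaires, but no vital signs. SAP Table 2 shows the same pattern, and SAP 8.4 takes baseline resting blood pressure from Screening. Beyond the schedule, 7.1.1 says that "at home blood pressure measurements may be required to corroborate or rule out undiagnosed hypertension", as an example of extra assessments at staff discretion.

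The next scheduled reading is on the morning of Visit 5. Table 8 puts it at about 9:55 and the initial dose at about 10:00. Section 7.3.1.1 attaches no action to its value. For the supplemental dose, the same section has the site physician told the recent vital signs and then approve or deny the dose.

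**The concern.** MDMA raises blood pressure in a dose-dependent way. Section 9.2.2.1 manages this by excluding uncontrolled hypertension and monitoring vital signs. The trial also admits people with treated, well-controlled hypertension (inclusion 11), and 9.2.2.1 says that the drug's effects in this group are still being characterized.

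Followed exactly as written, the plan confirms that exclusion 17 still does not apply from readings that may be weeks or months old. A rise without symptoms could go unmeasured until minutes before the first dose. The reading then taken is a single one, whereas exclusion 17 rests on repeated readings, so it cannot by itself show that the participant has become ineligible. Nothing requires anyone to take a second.

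The pre-dose value is also a reference. Return to pre-dose levels is one condition for ending the session (7.3.1.1), and safety objective 11 measures change from it (2.3). A high starting value makes both less informative.

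**Working it through.** **Step 1. The plan's own period lengths.** The plan gives no Screening-to-Visit 4 interval, so it has to be built from the periods.

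- Screening Period (Table 1): about 4 weeks, plus or minus 2, so 2 to 6 weeks = 14 to 42 days. This matches 4.2.
- Preparatory Period (Table 1): about 6 weeks, +5/−4, so 2 to 11 weeks = 14 to 77 days. This matches 4.2.
- Its lower limit is stated twice: "The Preparatory Period begins at enrollment and can be as brief as 2 weeks" (4.2) and "The minimum time to complete the Preparatory Period is 2 weeks" (7.2).
- Screening visits: 7 to 28 days. Then Independent Rater Screening 2 to 9 days later, then Visit 0 a further 2 to 14 days later (Table 1).

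**Step 2. The interval, one anchor at a time.**

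| Blood pressure taken at | Shortest | Longest |
|---|---|---|
| End of Screening visits | 2 + 2 + 14 = 18 days | 9 + 14 + 77 = 100 days |
| Start of Screening | 14 + 14 = 28 days | 42 + 77 = 119 days |

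In weeks: 18/7 = 2.6 and 100/7 = 14.3; 28/7 = 4 and 119/7 = 17. At the nominal lengths, the interval from the start of Screening is about 4 + 6 = 10 weeks.

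**Step 3. Are the extremes attainable?**

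- 18 days: the 14-day Preparatory Period works with Visit 0 on day 0, Visit 1 on day 0, Visit 2 on day 2, Visit 3 on day 10, Visit 4 on day 14 and Visit 5 on day 16. Visit 5 is then 14 days after Visit 2 and 6 days after Visit 3. Screening visits must last at least 14 − 4 = 10 days.
- 100 days: Screening visits must last no more than 42 − 9 − 14 = 19 days.
- 119 days: 4.2 caps participation at 27 weeks = 189 days. The shortest path from Visit 4 to Visit 15 is 1 + 21 + 42 + 1 = 65 days, so the latest Visit 4 is day 189 − 65 = 124.

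**Step 4. Other window conventions.** Visit windows alone allow 16 days from the end of Screening, but only with a 12-day Preparatory Period, below the stated 2 weeks. Adding every Screening maximum gives 28 + 9 + 14 = 51 days, and 51 + 77 = 128 days = 18.3 weeks, but this breaks the 6-week Screening limit. Neither changes the conclusion.

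**Step 5. What each result leads to.**

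| Result | Stated consequence |
|---|---|
| Positive drug screen before dosing | Site physician reviews; possible delay, rescheduling or withdrawal (7.3.1.1) |
| Positive pregnancy test before dosing | Withdrawal (7.3.1.1) |
| Temperature more than 1.5 °C above baseline despite cooling | Site physician consulted (9.2.3.1) |
| Vital signs before the supplemental dose | Site physician approves or denies (7.3.1.1) |
| Cardiac or neurological symptoms in session | Additional vital signs; physician notified (9.2.2.1) |
| Blood pressure before the initial dose | None tied to its value |

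**The case against.** The plan is not silent on continued eligibility. Eligibility is assessed at Visits 0, 1, 2 and 4 (Table 5). Each Preparatory Session asks about changes in health (7.2.1), and a participant whose health worsens after tapering is withdrawn (11.1). Extra readings are allowed at Screening, and Table 6 footnote F allows vital signs as needed during sessions. The general eligibility check in 7.3.1.1 and the stopping provision in 4.3.4 let the site withhold a dose. The physician is to be available by telephone (9.2). Nor are ECG and laboratory criteria routinely repeated, so continuing to meet a criterion need not mean measuring it again.

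All of that stands, and it rules out any claim that the site is powerless to act. It does not close the gap. Questions and symptom-prompted readings need not find an asymptomatic rise, and permission to repeat is not a requirement to do so.

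Several stronger readings are tempting but not supported:

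- A reader might quote 18 days to 17 weeks as one range. That joins the minimum from one anchor to the maximum from the other. The 17 weeks also needs a reading on the first Screening day, whereas the order recommended in 7.1.1 puts vital signs after the initial eligibility review.
- A reader might conclude that the go-ahead precedes the reading because it is listed first. The bullets are unnumbered, and Table 8 times are approximate.
- A reader might count all 80 sessions (40 × 2). By Visit 10 a participant has had blood pressure taken at Visit 5, 21 to 35 days earlier, and the physician is already consulted on dose. The unmeasured interval precedes Visit 5 only, where the initial dose is the lower one, 80 mg.
- A reader might argue from tapering, since "Medications will only be discontinued after enrollment per clinical judgment of the site physician in consultation with the prescribing physician". The documents do not say that tapering raises blood pressure.
- Weight (exclusion 26) is also not re-measured at Visit 4, but the documents state no resulting harm.

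**Conclusion.** The point holds as a procedural safety gap. Continued freedom from uncontrolled hypertension is required at Enrollment Confirmation but is not routinely measured there. The last scheduled reading is 18 to 100 days old if taken at the end of Screening, or 28 to 119 days old if taken at the start. The next is a single reading about five minutes before the first dose, and no value of it requires a repeat or review. This applies to every participant, up to 40 as planned; 4.3.4 allows some replacement, so the number of first sessions could be slightly higher.

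The intervals assume the Preparatory Period runs from Visit 0, as 4.2 says. The Table 1 heading counts it from Visit 1, which can fall up to 12 days after Visit 0 and would lengthen the maxima by that much. The documents give no rate of blood pressure change over this interval, so the number of participants affected cannot be estimated. Nothing here bears on the CAPS-5 or SDS analyses.

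**What to change.** 1. Add blood pressure and pulse to the Visit 4 column of Table 5 and to the list in 7.2.3, with a repeat if blood pressure is elevated, because exclusion 17 depends on repeated readings. Carry the tick into SAP Table 2; the SAP 8.4 baseline can stay at Screening.
2. In 7.3.1.1, require that a pre-dose reading of at least 140 mmHg systolic or 90 mmHg diastolic be repeated and reviewed by the site physician before the initial dose. This matters chiefly at Visit 5. The values are exclusion 17's own and serve only to trigger the repeat and review; they are not a dosing cut-off, and the decision stays with the physician.

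The cost is a few minutes at an existing 3-hour visit, a physician call when the reading is high, and an occasional delayed session. At Visit 10 the call can be combined with the existing consultation on dose.
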